## 6. Measures and Procedures

### 6.1. Informed Consent

Signed informed consent will not be required for participation in this study because the act of voluntarily participating in the online enrollment process is considered implied consent. However, participants will be required to check a box during the eligibility process assenting to the Summary Explanation of Research document, which will describe the study in detail including the rights of the research participant and potential risks associated with study participation. This document will inform potential participants that a Certificate of Confidentiality was requested and granted by the National Institutes of Health in order to protect the research team from being forced to share court ordered information about participants. Participants will also assent by checking a box to allow Highmark Health to provide the MyNewOptions study investigators with participant contraceptive pharmacy claims and health care utilization claims occurring 6 months prior to study enrollment through the end of the 2-year study period.

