### 11.2.3.2. Contraceptive adherence

Contraceptive adherence will be classified as high, medium, and low using self-report and pharmacy claims data, depending on the type of contraception being used. For women who have had a sterilization procedure (male or female) or LARC initiation since study enrollment, adherence will be categorized as high. For coital-dependent methods, standard self-reported adherence measures will be used to define adherence categories as shown in Table 3.

Table 3. Definition of Contraceptive Adherence

Methods	Measurement	Definitions	Adherence Category
Sterilization or LARCs (i.e., IUD, contraceptive implant)	Self-report	Adherence assumed	High
Coital dependent methods (i.e., spermicides, withdrawal, sponge, condoms, diaphragm, fertility awareness methods)	Self-report: What percent of time did you use your birth control method during sex in the past 6 months?	Always (100%)	High
		Most of the time (71-99%)	Medium
		Often (51-70%)	
		Sometimes (31-50%)	Low
		Occasionally (1-30%)	
Never (0%)			
Oral contraceptives, contraceptive patch, contraceptive ring, DMPA	Pharmacy claims data: Medication Possession Ratio	MPR >90%	High
		MPR 80-90%	Medium
		MPR <80%	Low

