While self-report measures of oral contraceptive adherence have been the standard in research of this type, self-report has been poorly validated against electronic medication monitors and biochemical assays of medication metabolites. In light of this, we will measure adherence to prescribed contraceptives (i.e., oral contraceptives, patch, shot (DMPA), or ring) using *pharmacy claims data* through Highmark to determine medication possession ratios (MPR). The MPR is the sum of days supply for all prescription fills in the study period, divided by the number of days in the study period. Using pharmacy claims data in this manner can help characterize poor adherence to prescribed medications, including hormonal contraceptives. Since direct observation of medication use is not possible in this study, acquisition of timely refills serves as an appropriate surrogate. Medication adherence has generally been accepted to be an MPR>80%, however this is likely too low when studying contraception. Thus, we will define high (MPR>90%), medium (80-90%), and low adherence (<80%) categories. Highmark preliminary data shows that 6% of members disenroll annually. For participants who are no longer enrolled in Highmark, we will be unable to obtain MPR data for prescription contraceptives. In those cases we will use retrospective self-report measures on contraceptive compliance over the past 6 months. A recent study shows that retrospective report of oral contraceptive use in this manner is equivalent to prospective medication diaries.

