#### **11.2.4. Other Outcomes**

##### **11.2.4.1. Unintended pregnancy**

The incidence of unintended pregnancies throughout the 2-year study period will be studied as an exploratory outcome measure. At each follow-up assessment, participants will be asked if they have been pregnant in the past 6 months since the previous assessment. We will be able to define pregnancies as intended or unintended based on *prospective* measurement, which is a major strength of this longitudinal approach. Incident pregnancies will be considered intended if the woman reported intending pregnancy in the next year at the preceding interview, and unintended if she stated she was not intending pregnancy in the next year. Traditional measures of pregnancy intention have been criticized for being measured retrospectively, where women are asked after they have given birth to think back to before they got pregnant and recall whether or not they were intending pregnancy at that time. Our previous work has demonstrated that prospective measurement of pregnancy intention strongly predicts future pregnancy over a 2-year period. We will measure the unintended pregnancy rate in each of the 3 study groups in 2 ways: 1) the proportion of pregnancies that are unintended (49% of pregnancy unintended in U.S.) and 2) the incidence of unintended pregnancies per 1000 women per year (there were 51 unintended pregnancies per 1000 U.S. women per year in 2001).

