For the ordinal outcome variable of contraceptive method, we will code it for each participant as 0 (no method), 1 (less effective method), 2 (more effective method), or 3 (most effective method), and we will construct an average score for each participant across those time periods in which the participant is not intending pregnancy. We will apply a weighted regression analysis to these average scores, in which the weighting factor for a participant is the variance of her estimated average. Then the statistical analysis will proceed in a similar manner to that described above for the binary outcomes, and we will embed an ordinal logistic regression model with random participant effects to investigate if there are time period effects and/or time period by intervention interactions.

[figure not shown]
#### 11.3.2. Specific Aim 2

The outcome variables are ordinal (continuity of contraceptive use; contraceptive adherence), and will be measured at four time periods post-baseline (6, 12, 18, and 24 months). For the contraceptive continuation, we will code it for each participant as 0 (continuous non-use), 1 (non-continuous use with gaps when at risk for pregnancy), 2 (non-continuous use with gaps when not at risk for pregnancy), 3 (continuous use with at least one method switch), or 4 (continuous use of one method). For the contraceptive adherence variable, we will code it for each participant as 0 (none), 1 (low), 2 (medium), or 3 (high). We will analyze these ordinal outcomes in the same manner as described above for the ordinal outcome in Specific Aim 1.

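### The medication possession ratio (MPR) formula and the Aim 2 analysis use different windows, and over the six months the analysis needs, summing fills misclassifies late refillers and can leave Medium empty

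*Protocol*

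**What the plan says.** Protocol section 11.2.3.2 gives the formula: "The MPR is the sum of days supply for all prescription fills in the study period, divided by the number of days in the study". The window named in both numerator and denominator is the study period. The numerator has no term for supply on hand at the start, and nothing cuts off supply that runs past the end. The same section fixes the classes: "we will define high (MPR>90%), medium (80-90%), and low adherence (<80%) categories". Table 3 applies this measure to one group of methods, "Oral contraceptives, contraceptive patch, contraceptive ring, DMPA", with pharmacy claims as the source.

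The window is not consistent. Section 11.2.4.1 speaks of pregnancies "throughout the 2-year study period", and section 6.1 also gives the study period as 2 years. Section 11.3.2 says that the Aim 2 outcomes, adherence among them, "will be measured at four time periods post-baseline (6, 12, 18, and 24 months"). It codes adherence 0 to 3 and analyses it like the ordinal outcome of Aim 1, that is, as each woman's average over periods. The self-report fallback in 11.2.3.2 for women who leave the insurer looks back 6 months.

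Section 6.1 obtains "participant contraceptive pharmacy claims and health care utilization claims occurring 6 months prior to study enrollment" onward, so both earlier fills and utilization claims will be in hand.

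**The concern.** Adherence is one of the two outcomes that section 11.2.3 names as primary for Aim 2, and section 7.3 gives better adherence as the objective of the action-planning component. The behaviour at issue is largely whether refills are late.

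Two things look wrong. First, one MPR over 2 years gives one value per woman and cannot supply four time points, so 11.2.3.2 and 11.3.2 cannot both be followed as written. Second, under the six-month reading that the analysis requires, the ratio moves in steps of one whole fill. For several fill sizes the step is wider than the 80-90% band. A woman's class then depends partly on where her fill dates fall relative to the interval boundaries.

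**Working it through.** The protocol states no worked MPR or class frequency, so there is no figure of its own to reproduce.

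**Inputs.** Formula and cut-offs: 11.2.3.2. Time points: 11.3.2. Window W: six months, 181-184 days, taken as 182. Fill size d: 90 days appears in the protocol (mail-order supplies, section 7.3). The sizes 28, 30 and 84 days are assumptions.

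**Step 1. Reachable values, MPR = k × d / W with k whole fills, W = 182.**

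| Fill size | Values either side of, or in, the band | Medium reachable? |
|---|---|---|
| 28 | 5 × 28/182 = 76.9%; 6 × 28/182 = 92.3% | No |
| 84 | 1 × 84/182 = 46.2%; 2 × 84/182 = 92.3% | No |
| 90 | 1 × 90/182 = 49.5%; 2 × 90/182 = 98.9% | No |
| 30 | 5 × 30/182 = 82.4% | Yes |

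The three negative results hold at every W from 181 to 184. Medium returns for 28- and 84-day fills at W = 187-210, and for two 90-day fills from W = 200. Some mixtures also reach it: (2 × 28 + 90)/182 = 80.2%.

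**Step 2. The literal 2-year window, W = 730.** Medium is reachable: 21 × 28/730 = 80.5% to 23 × 28/730 = 88.2%; 7 × 84/730 = 80.5%; 7 × 90/730 = 86.3%. But this reading gives one value per woman, not four.

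**Step 3. Constant coverage c, random starting phase.** The refill gap is d/c, so the mean number of fills in the window is W × c/d, and its fractional part is the chance of the higher count.

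- On time (c = 1): 182/28 = 6.5, 182/84 = 2.17, 182/90 = 2.02. At least six, two and two fills always fall inside, so the class is always High.
- c = 0.85, truly Medium: 154.7/28 = 5.525, so 52.5% High and 47.5% Low; 154.7/84 = 1.842, so 84.2% High and 15.8% Low; 154.7/90 = 1.719, so 71.9% High and 28.1% Low. None are Medium.
- c = 0.95, truly High, 90-day fills: 172.9/90 = 1.921, so 7.9% are scored Low.

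**Step 4. Carry-in example.** One 90-day fill inside the window plus 80 days carried in scores 90/182 = 49.5% (Low), although (90 + 80)/182 = 93.4% was available (High).

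**Step 5. Irregular refills.** Simulation of 40,000 women per scenario, with an exponential delay after each supply runs out. Class from fills dated in the 182-day interval is compared with class from days covered.

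| Fill size | Mean delay | Intervals with a different class |
|---|---|---|
| 28 | 3 days | 44% |
| 28 | 7 days | 52% |
| 30 | 3 days | 41% |
| 30 | 7 days | 38% |
| 84 | 3 days | about 2% |
| 90 | 7 days | about 31% |

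In the last row about 11% of truly High women are scored Low.

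**Step 6. Effect on the analysed quantity.** Four intervals per woman, scores averaged, groups with mean delays of 4 and 7 days. The standardised group difference is shown as fill-sum against days covered.

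| Fill size | Delay varies between women | No variation between women |
|---|---|---|
| 28 | 0.43 v 0.43 | 2.11 v 2.33 |
| 30 | 0.53 v 0.50 | not run |
| 84 | 0.31 v 0.40 | 0.45 v 1.16 |
| 90 | 0.41 v 0.46 | 0.52 v 1.09 |

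**The case against.** The strongest reply is that the six-month window is inferred and the pack sizes are mostly assumed. Both points stand. The formula says study period, and over 2 years the Medium class is reachable. Only 90-day supplies appear in the protocol. Use of 30-day fills, some mixed fills, or survey-to-survey intervals stretched by the weekly reminders of section 5.2.3 would populate Medium. It therefore cannot be said that the scale has only two levels for all women. This does not rescue the formula: the 2-year reading cannot feed the four-time-point analysis, and 30-day fills still disagree with days covered in about 40% of intervals.

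A reader might infer from 44% or 52% interval misclassification that the comparison of RLP, RLP+ and control is badly blurred, or biased. The documents do not support that. The analysed score is an average over periods, so many errors cancel; for 28-day fills the standardised difference hardly changes. The rule is identical in all arms, so no direction of bias is built in unless the arms differ in fill size or method mix. Nor does omitting carry-in penalise women who refill on time.

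It can also be said that carry-in and overlap rules belong in a statistical analysis plan, which is not at hand, and that MPR is an accepted measure with cited precedent. That would answer a silent protocol. This one fixes the formula, the cut-offs and the data source, so an analysis plan that follows it inherits the defect and one that repairs it departs from the protocol.

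Finally, the MPR covers only pill, patch, ring and DMPA users still enrolled with the insurer, and adherence belongs to the secondary aim and does not drive the sample size. This limits the reach of the point.

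**Conclusion.** The point holds in this form. Sections 11.2.3.2 and 11.3.2 do not agree on the MPR window. Under the six-month window that the analysis needs, the fill-sum formula cannot return Medium for women who fill only 28-, 84- or 90-day units, and it misclassifies women who refill late at every fill size examined.

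The size depends on fill sizes and delays that the protocol does not give. At the interval level, disagreement ranges from about 2% (84-day, mean delay 3 days) to 52% (28-day, mean delay 7 days). For the averaged group contrast the loss is small with 28-day fills. It is material mainly for 84- and 90-day supplies: 0.31 against 0.40 and 0.41 against 0.46 when delay varies between women, and more when it does not. The consequence is lost information in an Aim 2 primary outcome, not a biased treatment effect. These results assume continuing users, exponential or constant refill delay, and a 182-day interval.

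**What to change.** In section 11.2.3.2 and Table 3:

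- State that the window is each 6-month assessment interval.
- Replace the fill-sum MPR with the proportion of days covered in that interval. Count supply remaining from earlier fills, carry overlapping supply forward, and cut off supply that runs past the interval end.
- For the first interval, take carry-in from the claims for the 6 months before enrollment.
- Keep the 80% and 90% cut-offs.
- If DMPA is billed as a clinic procedure (an assumption; the protocol does not say), also take administrations from the utilization claims already obtained.

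Under this rule, with constant refill gaps, a woman with 85% coverage is classed Medium in 100% (28-day), 92% (84-day) and 83% (90-day) of starting phases, against 0% under the present formula. At 95% coverage with 90-day fills she is always High. Some phase dependence remains for long supplies.

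The cost is a wording change and programming on data the study will already hold. The one drawback is that results compare less directly with published MPR values.

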#### **11.2.4. Other Outcomes**

##### **11.2.4.1. Unintended pregnancy**

The incidence of unintended pregnancies throughout the 2-year study period will be studied as an exploratory outcome measure. At each follow-up assessment, participants will be asked if they have been pregnant in the past 6 months since the previous assessment. We will be able to define pregnancies as intended or unintended based on *prospective* measurement, which is a major strength of this longitudinal approach. Incident pregnancies will be considered intended if the woman reported intending pregnancy in the next year at the preceding interview, and unintended if she stated she was not intending pregnancy in the next year. Traditional measures of pregnancy intention have been criticized for being measured retrospectively, where women are asked after they have given birth to think back to before they got pregnant and recall whether or not they were intending pregnancy at that time. Our previous work has demonstrated that prospective measurement of pregnancy intention strongly predicts future pregnancy over a 2-year period. We will measure the unintended pregnancy rate in each of the 3 study groups in 2 ways: 1) the proportion of pregnancies that are unintended (49% of pregnancy unintended in U.S.) and 2) the incidence of unintended pregnancies per 1000 women per year (there were 51 unintended pregnancies per 1000 U.S. women per year in 2001).

##### **11.2.4.2. Satisfaction with each condition**

We will assess participant satisfaction with each of the 3 conditions and how easy they were to use.

### 11.3. Analytic Methods

#### 11.3.1. Specific Aim 1

The outcome variables are binary (contraception use; satisfied with contraceptive method) and ordinal (contraceptive method effectiveness), and will be measured at four time periods post-baseline (6, 12, 18, and 24 months). For the binary outcome variables, we will construct a proportion for each participant as the number of time periods in which the participant's response is positive, divided by the number of time periods in which the participant is not intending pregnancy. The denominator will be four, except for those participants who withdraw consent from the study, change their minds about intending pregnancy during the study, or become pregnant. Therefore, we will apply a binomial regression analysis to these proportions. We will use intervention group assignment (intention-to-treat analysis) as the sole regressor in the primary analysis, but we will investigate in secondary analyses the effects of selected covariates on the proportional response (demographics; pregnancy history; sexual and contraceptive history; perceived control/fatalism toward contraception; relationships; compliance with log-in requirements). In terms of the three randomized groups, we will construct two-sided test statistics for comparing: 1) RLP to control, 2) RLP+ to control, and 3) RLP to RLP+. Therefore, we will impose a Bonferroni correction factor to the significance level ( $\alpha = 0.0167$ ). We will apply additional secondary analyses that are longitudinal, in which we invoke a logistic regression model with random participant effects to investigate if there are any time period effects and/or time period by intervention interactions for the binary outcomes. Finally, we will invoke a shared parameter model to account for the informative censoring that could occur due to participant withdrawal in a longitudinal study. In our setting, the shared parameter model includes a Weibull time-to-event regression model for the time to participant withdrawal in conjunction with a logistic regression model with random participant effects for the binary outcome.

For the ordinal outcome variable of contraceptive method, we will code it for each participant as 0 (no method), 1 (less effective method), 2 (more effective method), or 3 (most effective method), and we will construct an average score for each participant across those time periods in which the participant is not intending pregnancy. We will apply a weighted regression analysis to these average scores, in which the weighting factor for a participant is the variance of her estimated average. Then the statistical analysis will proceed in a similar manner to that described above for the binary outcomes, and we will embed an ordinal logistic regression model with random participant effects to investigate if there are time period effects and/or time period by intervention interactions.

[figure not shown]
#### 11.3.2. Specific Aim 2

The outcome variables are ordinal (continuity of contraceptive use; contraceptive adherence), and will be measured at four time periods post-baseline (6, 12, 18, and 24 months). For the contraceptive continuation, we will code it for each participant as 0 (continuous non-use), 1 (non-continuous use with gaps when at risk for pregnancy), 2 (non-continuous use with gaps when not at risk for pregnancy), 3 (continuous use with at least one method switch), or 4 (continuous use of one method). For the contraceptive adherence variable, we will code it for each participant as 0 (none), 1 (low), 2 (medium), or 3 (high). We will analyze these ordinal outcomes in the same manner as described above for the ordinal outcome in Specific Aim 1.

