##### 3.1.2. Secondary Hypotheses

Compared with random assignment to an information only control group, random assignment to a reproductive life planning tool (RLP) or a reproductive life planning tool plus a contraceptive action planning tool (RLP+) will:

- Lead to the use of more effective contraception
- Result in more continuous use and better method adherence during the two year study period.
- Improve contraceptive method satisfaction
- Result in lower rates of unintended pregnancy (exploratory outcome)

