### 11.2.2.2. Satisfaction with contraceptive method

A validated 5-item contraceptive satisfaction measure will be used that measures satisfaction with ease of use, effectiveness, side effects, cost, and overall satisfaction. Additional validated items will be included to indicate satisfaction with partner support of the contraceptive method.

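### The satisfaction proportion in section 11.3.1 keeps periods without a method in its denominator, so it measures using a method and being satisfied with it, and a rise in use alone would raise it

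*Protocol*

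**What the plan says.** Section 3.1.2 lists "Improve contraceptive method satisfaction" as a secondary hypothesis. The primary outcome, in section 3.1.1, is use of any method.

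Section 11.2.2.2 gives the instrument: "A validated 5-item contraceptive satisfaction measure will be used". Its items rate the method itself (convenience, efficacy, side effects, cost) and include an overall rating.

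Section 11.3.1 fixes the analysis. It names "satisfied with contraceptive method" as one of two binary outcomes, the other being contraceptive use. One rule serves both outcomes. The numerator counts the periods with a positive response, and this count is "divided by the number of time periods in which the participant is not intending pregnancy". On the size of that denominator the section says: "The denominator will be four, except for those participants who withdraw consent from the study". Two further exceptions follow, a changed intention about pregnancy and a pregnancy. No other exception is given.

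The protocol does not say in words who answers the satisfaction items or how a period without a method is recorded. For method effectiveness, section 11.3.1 does give non-use an explicit code of 0. It gives none for satisfaction.

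**The concern.** The rule suits contraceptive use, where a period of non-use is a genuine negative. For satisfaction with a method, a woman who has no method has nothing to rate. Under the same rule her period still counts in the denominator and adds nothing to the numerator. Non-use is foreseen: section 7.2 accepts that a participant may choose no method, and she stays in the trial.

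The satisfaction variable then contains the primary outcome as a factor. If an intervention raises use and changes nothing else, the variable rises. Read against section 3.1.2, that would be reported as better satisfaction with the method, as a finding separate from use, when it is the same finding seen twice. A fall in satisfaction among users could also be hidden by a rise in use.

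**Working it through.** The protocol gives no planning figure for satisfaction, so there is none to reproduce. The check needs only the rule in section 11.3.1.

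**Notation.** Among periods not intending pregnancy in one arm, let *u* be the share with a method, *s* the share of those periods in which the woman is satisfied, and *f* the share of periods without a method that are counted as positive.

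**Plan's measure.** P = u·s + (1 − u)·f.

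**Difference between arms** when *s* and *f* are the same in both, so that there is no effect on satisfaction: P₁ − P₀ = (s − f)·(u₁ − u₀).

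The method-specific items in section 11.2.2.2 make *f* = 0 the natural reading, and the difference becomes s·(u₁ − u₀). It vanishes only if use is equal in the arms or if non-users score positive as often as users do.

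**Inputs.** The values of *s* from 0.6 to 0.9 are assumed, as are use of 0.80 vs 0.90 and 0.90 vs 0.95. The pair 0.25 vs 0.35 is the planning difference for the binary outcomes in section 3.2, applied here to use.

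| Use, control vs intervention | s | Plan's measure | Difference | Difference over periods with a method |
|---|---|---|---|---|
| 0.25 vs 0.35 | 0.8 | 0.20 vs 0.28 | 0.08 | 0 |
| 0.80 vs 0.90 | 0.6 | 0.48 vs 0.54 | 0.06 | 0 |
| 0.80 vs 0.90 | 0.8 | 0.64 vs 0.72 | 0.08 | 0 |
| 0.80 vs 0.90 | 0.9 | 0.72 vs 0.81 | 0.09 | 0 |
| 0.90 vs 0.95 | 0.6 | 0.54 vs 0.57 | 0.03 | 0 |
| 0.90 vs 0.95 | 0.9 | 0.81 vs 0.855 | 0.045 | 0 |

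The difference depends on the gain in use and not on its starting level, so any 10-point gain gives 6 to 9 points over this range of *s*. For comparison, the effect planned for in section 3.2 is 10 points.

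**Opposite directions.** Suppose use rises from 0.80 to 0.90, existing users are 80% satisfied, and the added users are 50% satisfied (all assumed). The plan's measure goes from 0.80 × 0.80 = 0.64 to 0.64 + 0.10 × 0.50 = 0.69, a gain of 5 points. Satisfaction among users goes from 0.80 to 0.69 / 0.90 = 0.77, a fall of about 3 points.

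**The case against.** The strongest defence is that the all-periods denominator is the right one for a randomised comparison. It compares arms as assigned, in keeping with the intention-to-treat analysis in section 11.3.1, and asks a sensible question: are more women using a method they are content with? Restricting to users would select on something that happens after randomisation. This stands. It is a reason to keep the variable and name it correctly, but it does not make the variable a measure of satisfaction with the method.

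It can also be said that the effect appears only if use really rises. Section 3.1.1 counts any method, including withdrawal and natural family planning, so use may be near its ceiling and the gain small. Use is reported by arm anyway, so an attentive reader could see the source. Both points limit the size of the problem. Neither removes it.

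A reader might infer more than the protocol supports:

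- *That the protocol says non-users are scored as not satisfied.* It does not say so. This follows from the denominator rule and its list of exceptions, and would fail if non-users could answer positively or if their periods were in fact left out.
- *That the absence of a cut-point for satisfied is an error.* Such a detail may sit in the statistical analysis plan, which is not at hand.
- *That reducing the scale to yes or no loses a known share of the information.* Any such figure assumes a total score with a particular distribution. The protocol describes no total score, and the binary variable could come from the overall item alone.
- *That the satisfaction hypothesis is untestable.* The composite is informative. It cannot carry that hypothesis by itself.

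**Conclusion.** The point holds as an error of labelling and interpretation on one secondary outcome. Under section 11.3.1 as written, the satisfaction proportion equals use times satisfaction among users. With no change in satisfaction among users, it rises by 6 to 9 points for a 10-point rise in use, and by 3 to 4.5 points for use of 90% vs 95%.

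This rests on three assumptions: periods without a method are never positive, 60% to 90% of users are satisfied, and that share is equal in the arms. The use rates are illustrative. If use does not differ between arms, there is no distortion. The primary outcome and its analysis are not affected. The correction should be made because the rule is stated in the protocol and bears on a named hypothesis.

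**What to change.** 1. In sections 11.2.2.2 and 11.3.1, state how a period without a method counts. Keep the present variable as an intention-to-treat composite and name it 'using a method and satisfied with it'.
2. State that the composite is not, on its own, evidence for the satisfaction hypothesis in section 3.1.2.
3. Add a supportive analysis of satisfaction over periods with a method, using the scale already collected. Average within participant and give more weight to participants who contribute more periods. Section 11.3.1 already plans weighted regression of participant averages for the ordinal outcome, so no new kind of method is needed.
4. Report both results beside the share using a method in each arm, so that the two components can be seen.

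The cost is some wording and one further analysis, with no new data. The drawback is that the users-only comparison conditions on use after randomisation. It is not a clean randomised contrast and must be labelled supportive.
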